5.2 Methods

The neonIN surveillance network captures data on episodes of invasive neonatal infection on a web-based database (www.neonin.org.uk). Over 30 UK neonatal units currently contribute to this database in real-time. An episode of neonatal infection is defined as a positive culture collected from a normally sterile site such as the blood, cerebrospinal fluid (CSF) or urine (via catheter or suprapubic aspirate) for which clinicians prescribed at least five days of appropriate antibiotics. Clinical, demographic and microbiological data (including antimicrobial susceptibilities) are collected using a standardised online questionnaire. Denominator data regarding the total number of live-births and neonatal-admissions are collected for each neonatal unit.

For the purpose of this study data will be entered onto an electronic data collection tool or web based database related to information on the baby's status at 28 days after the positive culture was obtained.

If the baby is alive, then this baby becomes eligible as a control. If the baby has died, then further details will be sought including the date of death and whether the infection was associated with the baby's death. Babies with positive cultures, but who have died before receiving 5 days of appropriate antimicrobial therapy (currently a component of the surveillance case definition), will also be captured prospectively.

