4.2 Secondary aim

- In a case-control study we will assess the hypothesis that babies who die from bacterial infections on neonatal units do so because they receive inappropriate antibiotic management. To do this we will compare babies who die from bacterial infections with babies who survive bacterial infections on a range of factors including appropriateness, dose and timeliness of antibiotic use.

5 STUDY DESIGN and METHODS of DATA COLLECTION and DATA MANAGEMENT

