5.3 Data collection

Invasive infection episodes will be captured prospectively on a web-based infection surveillance database called neonIN (www.neonin.org.uk) which is coordinated by [name] at St George's University of London. The neonIN network currently includes 30 NNUs. For the purposes of this project all centres that wish to participate in neoAMRO will have access to the electronic data collection tool or web based database and will capture anonymised data regarding invasive episodes of infection.

For the purposes of the neoAMRO study, information on the baby's status at 28 days after the positive culture will be collected (alive / died / not known). If the baby is alive, then this baby becomes eligible as a control. However, if the baby has died, then further details will be sought including the date of death and whether the infection was believed to be associated with the baby's death. Babies with positive cultures but who have died before receiving 5 days of appropriate antimicrobial therapy (currently a component of the surveillance case definition), will also be captured prospectively.

Thus, the following data will be collected as part of the neoAMRO study:

- outcome at 28 days (alive / died / not known)
- date of death
- cause of death (if association with infection)
- antibiotics: name / start date / dose / frequency / stop date
- whether antibiotic regime was changed during therapy
- reason for change in antibiotic regime
- new antibiotics: name / start date / dose / frequency / stop date

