7 SAMPLE AND RECRUITMENT

7.1 Eligibility Criteria

There will be no exceptions (waivers) to eligibility criteria for data inclusion into the study.

The criteria have been carefully considered and are standards used to ensure the data can be appropriately selected, collected and appropriately analysed. It is therefore vital exceptions are not made to the following detailed selection criteria.

- Infants on participating NNUs who have an episode of infection with a positive culture.

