7.3 Recruitment

7.3.1 Participant identification

Eligible babies are those in whom a positive culture has been obtained. Records will be identified by the local clinical team at each participating unit. The local team consisting of Neonatologists and research Nurses will then enter the relevant details onto an electronic data collection tool or web-based database, as part of their routine clinical duties. Data will be entered retrospectively on a regular basis either (weekly/monthly) depending on the unit activity and in compliance with the duties of the local team.

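### The five-day appropriate-antibiotic rule applies to survivors but is lifted for deaths, so controls are selected partly on the exposure that the secondary case-control aim tests

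*Protocol*

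**What the plan says.** Section 5.2, and the Study Design entry of the Study Summary in the same terms, defines an episode as a positive culture from a normally sterile site "for which clinicians prescribed at least five days of appropriate antibiotics".

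Controls come from the captured episodes: "If the baby is alive, then this baby becomes eligible as a control". Deaths have a second route into the study. Section 5.2 says that culture-positive infants "who have died before receiving 5 days of appropriate antimicrobial therapy (currently a component of the surveillance case definition), will also be captured prospectively", and section 5.3 repeats this. No sentence gives survivors a similar route.

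The secondary aim (section 4.2) compares deaths with survivors "on a range of factors including appropriateness, dose and timeliness of antibiotic use".

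The eligibility statements differ. Section 7.1, which allows no waivers, requires "Infants on participating NNUs who have an episode of infection with a positive culture", and so relies on the term that section 5.2 defines. Section 7.3.1 is looser: "Eligible babies are those in whom a positive culture has been obtained". Section 6 also describes eligible babies by positive culture alone.

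Section 7.2.1 plans two controls per case, matched on birthweight category and hospital. Its power example concerns isolate susceptibility to empiric antibiotics: 80% in cases against 95% in controls.

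**The concern.** In a case-control study, controls should show how common the exposure is in the population that gave rise to the cases. Here a survivor for whom five days of appropriate antibiotics were never prescribed is not an episode and cannot be a control. A baby with the same treatment who died is a case. Entry depends on appropriateness in one group only, and appropriateness is the exposure under test.

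The likely effect is too few inappropriately treated babies among the controls, and so an odds ratio pushed towards the study hypothesis. Matching on birthweight category and hospital does not remove this. Nor does the multivariable logistic regression in section 7.2.1, because no model can restore survivors who were never entered. For the same reason this cannot be left to a later analysis plan.

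A smaller form of the same asymmetry concerns contaminants. Section 7.2.1 expects about half of the infections to be coagulase-negative staphylococci. The five-day rule also acts as a filter for infections judged worth treating, and that filter is likewise lifted only for deaths.

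**Working it through.** **The plan's own figure.** Inputs from section 7.2.1: 50 cases, 100 controls, susceptibility 80% v 95%, 5% significance (two-sided assumed), 80% power.

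- Pooled proportion: (50×0.80 + 100×0.95)/150 = 0.90.
- Standard error under no difference: √[0.90×0.10×(1/50 + 1/100)] = 0.0520.
- Standard error under the alternative: √[0.80×0.20/50 + 0.95×0.05/100] = 0.0606.
- z = (0.15 − 1.96×0.0520)/0.0606 = 0.79, so power is 78.7%.

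This agrees with the stated 80%, so the sample-size figure is not at fault. As mismatch the contrast is 20% v 5%, an odds ratio of (0.20/0.80)/(0.05/0.95) = 4.75.

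**Effect of the entry rule.** Call a baby mismatched if the isolate is not susceptible to the initial antibiotics. Let p be the mismatch rate among all survivors. Let f be the fraction of mismatched survivors who fail the five-day rule, and g the fraction of matched survivors who fail it. All deaths are kept.

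- Control odds of mismatch before selection: p/(1−p).
- After selection: p(1−f)/[(1−p)(1−g)].
- Observed odds ratio = true odds ratio × (1−g)/(1−f).

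The documents give neither f nor g, so the values below are assumptions. For p, 10% and 20% are the ends of the range in section 2; section 1 gives 5–16%. Example with p=10%, f=50%, g=25%: control mismatch is 0.050/(0.050 + 0.675) = 6.9%, and the odds ratio is (0.10/0.90)/(0.050/0.675) = 1.5 with no true effect.

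The rejection rates are for a 5% Pearson chi-square test with 50 cases and 100 controls and no true association. They come from exact enumeration, with the matching ignored.

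| f | g | Factor | Control mismatch, p=10% | Rejection | Control mismatch, p=20% | Rejection |
|---|---|---|---|---|---|---|
| 50% | 50% | 1.0 | 10.0% | 5% | 20.0% | 5% |
| 25% | 0 | 1.33 | 7.7% | 8% | 15.8% | 11% |
| 50% | 25% | 1.5 | 6.9% | 11% | 14.3% | 16% |
| 50% | 0 | 2.0 | 5.3% | 20% | 11.1% | 33% |

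**Which exposures are affected.** If the exposure is that no appropriate course of at least five days was ever prescribed, then f=100% by definition and no control can be exposed. If the exposure is initial empiric mismatch, late treatment or dose, a survivor whose regimen was corrected and then prescribed for five days still qualifies. In that case f is below 100% and may be well below it.

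**The case against.** The strongest reply has four parts.

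- **The provision for deaths has a good purpose.** A baby who dies on day 2 cannot have received five days of treatment. Without the provision the most relevant cases would be lost. This stands: the fault is not that early deaths are captured, but that survivors are still held to the rule.
- **Sections 6 and 7.3.1 admit any positive culture.** On that reading the asymmetry disappears. But section 7.1 uses the defined term, and separate capture of early deaths would be needless if every positive culture qualified. At the least, sites could apply different rules.
- **Mismatched survivors do enter.** The plan itself expects 5% non-susceptibility among controls, and section 5.3 records regimen changes with dates. This stands and limits the bias in the one comparison that is quantified. A reader might infer that control exposure is zero by construction. That holds only for never having been prescribed an appropriate course. The rule also turns on what was prescribed, so a survivor need not have completed five days.
- **The size has no anchor.** This stands. With g=0 and f=75% the factor would be 4.0, close to the planned 4.75, but nothing in the protocol suggests that so many mismatched survivors never had an appropriate course prescribed. Some matched survivors will also fail the rule, for instance where a probable contaminant was treated briefly. So g need not be zero, and g above f would reverse the direction.

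A reader might also infer that the primary aims suffer because numerator and denominator follow different rules. Section 4.1 does not support this: those aims describe babies who died and need no denominator. Case fatality appears only as a planning input in section 7.2.1.

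Contaminant deaths are partly handled, since sites record whether infection was associated with death and section 7.2.1 sets a 10-day cut-off for attributable mortality. But section 7.2.1 also compares all deaths within 28 days of a positive culture.

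**Conclusion.** The concern holds for the secondary case-control aim. As the protocol is most naturally read, control entry depends on appropriateness of antibiotics and case entry does not. The comparison is therefore likely to favour the hypothesis.

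The direction rests on mismatched survivors failing the rule more often than matched ones (f>g). That is plausible because the rule itself requires appropriate treatment, but the documents do not show it. The size is unknown. On the assumed values above, a true odds ratio of 1 would appear as 1.33 to 2.0, or stay at 1 if f=g. The bias is greatest for ever having been prescribed an appropriate course, and smaller for initial mismatch, timeliness and dose. Separately, the eligibility wording is inconsistent and needs correction whichever reading was intended.

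**What to change.** 1. Keep the capture of early deaths.
2. Apply one entry rule to deaths and survivors that does not depend on appropriateness or duration of antibiotics: for example, a positive sterile-site culture with a treatment course started with any agent.
3. Record appropriateness and duration only as exposures, classified in the same early window after the culture in both groups.
4. Apply the same true-infection criterion to both groups, including babies who die before day 5.
5. Reconcile the Study Summary and sections 5.2, 5.3, 6, 7.1 and 7.3.1.
6. Where survivors already left out cannot be recovered, state the selection as a limitation and report a sensitivity analysis that applies the same restriction to cases and controls. That analysis answers a narrower question, because it drops the early deaths again.

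The cost is a protocol and data-form amendment plus additional survivor records. According to the Study Timeline, data collection began in August 2019, so some of these survivors would have to be identified retrospectively by the sites.

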5.3 Data collection

Invasive infection episodes will be captured prospectively on a web-based infection surveillance database called neonIN (www.neonin.org.uk) which is coordinated by [name] at St George's University of London. The neonIN network currently includes 30 NNUs. For the purposes of this project all centres that wish to participate in neoAMRO will have access to the electronic data collection tool or web based database and will capture anonymised data regarding invasive episodes of infection.

For the purposes of the neoAMRO study, information on the baby's status at 28 days after the positive culture will be collected (alive / died / not known). If the baby is alive, then this baby becomes eligible as a control. However, if the baby has died, then further details will be sought including the date of death and whether the infection was believed to be associated with the baby's death. Babies with positive cultures but who have died before receiving 5 days of appropriate antimicrobial therapy (currently a component of the surveillance case definition), will also be captured prospectively.

Thus, the following data will be collected as part of the neoAMRO study:

- outcome at 28 days (alive / died / not known)
- date of death
- cause of death (if association with infection)
- antibiotics: name / start date / dose / frequency / stop date
- whether antibiotic regime was changed during therapy
- reason for change in antibiotic regime
- new antibiotics: name / start date / dose / frequency / stop date

5.4 Data Handling

All data should be handled in accordance with the Data Protection Act 2018 (UK implementation of the EU General Data Protection Regulation (GDPR)).

[name] will be the responsible individual within St George's University of London. The study database will be stored on the server of St George's, University of London with the following technical specifications:

Security:

External website access is governed by a L7 application firewall, with additional host based firewall security. Administrative access to the server is via PKI (Public Key Infrastructure), not username and password, and is for nominated individuals only, authorised by the data holder. Access to the website is via a 256bit SSL certificate backed by a 4092bit server key.

Backup and DR:

System backup is performed by both a grandfather-father-son scheme and a host based FIFO imaging rotation. DR facilities at SGUL includes offsite replication and restoration of services at a secondary data centre. Users will have password controlled access to their own institution data, managed by a small number of administrator users located at SGUL. Regular full database dumps will be performed daily and encrypted on disk using a 4096bit key.

The electronic data collection tool will be password protected and stored securely on servers at St George's University of London and at participating sites. The study ID log which will link patient details to the study will be held only at the participating site.

6 STUDY SETTING

This is a multicentre observational study involving NNUs across the UK. Study personnel (Neonatologists and research Nurses) from these NNUs will identify eligible babies in whom a positive culture has been obtained. The local study teams will then enter the relevant details will be entered onto an electronic data collection tool or web based database, as part of their routine clinical duties. Data will be entered retrospectively on a regular basis either (weekly/monthly) depending on the unit activity and in compliance with the duties of the local team.

7 SAMPLE AND RECRUITMENT

7.1 Eligibility Criteria

There will be no exceptions (waivers) to eligibility criteria for data inclusion into the study.

The criteria have been carefully considered and are standards used to ensure the data can be appropriately selected, collected and appropriately analysed. It is therefore vital exceptions are not made to the following detailed selection criteria.

- Infants on participating NNUs who have an episode of infection with a positive culture.

7.2 Sampling

7.2.1 Size of sample

Based on our previous data collection (see ref. 2), at the end of the enhanced study period we would expect to have data on up to 800 babies with invasive neonatal infections, approximately 50% will be due to coagulase negative staphylococci (CoNS), approximately 25% will be early onset sepsis and approximately 200 will be Gram-negative sepsis. Based on our recent data for case fatality rates (18% for Gram-negative bacteraemia, 8% for Group B streptococcus, 5% for staphylococcal aureus), we would expect around 50 deaths in this cohort.

All babies who have died within 28 days of a positive culture will then be compared with babies who have survived at 28 days across a range of relevant clinical and demographic factors. For all cases and for two controls per case (selected centrally, based on birth in same birthweight category and in same hospital), this will be performed through collection of anonymised data including birth gestation, birth weight and age at infection, antimicrobials administered for that infection episode (and if changed), relapses, length of stay and attributable mortality at 10 days using a standardised case report form. With approximately 50 cases of death and 100 controls, we anticipate that we will be able to explore the relationship between initial antimicrobial therapy and isolate susceptibility, with outcome, with great certainty. For example, with this sample size we can demonstrate a difference between susceptibility to empiric antibiotics of 80% among cases (or less) to 95% among controls, with 95% significance and 80% power; a difference that is clinically meaningful. A 10-day cut-off for attributable mortality will be used as early mortality is assumed to be more likely a direct consequence of infection than late mortality. Other risk factors for death will be assessed in univariate and multivariable logistic regression analyses.

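### Controls are selected without regard to organism, although the protocol's own figures tie organism group to death: the susceptibility comparison is open to confounding and is short of Gram-negative controls

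*Protocol*

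**What the plan says.** Section 7.2.1 describes the expected cohort: "we would expect to have data on up to 800 babies with invasive neonatal infections", of whom "approximately 50% will be due to coagulase negative staphylococci (CoNS" and "approximately 200 will be Gram-negative sepsis". The fatality rates it uses are "18% for Gram-negative bacteraemia, 8% for Group B streptococcus, 5% for staphylococcal aureus"; none is given for CoNS. From these it concludes that "we would expect around 50 deaths in this cohort".

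Cases are defined by outcome only, whatever the organism: "All babies who have died within 28 days of a positive culture will then be compared with babies who have survived at 28 days". Controls are "two controls per case (selected centrally, based on birth in same birthweight category and in same hospital". Sections 5.2 and 5.3 make any baby alive at 28 days eligible as a control. No section matches or restricts controls by organism.

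The power example is 80% susceptibility to empiric antibiotics in 50 cases against 95% in 100 controls. Section 7.2.1 then plans univariate and multivariable logistic regression for other risk factors and does not name organism. The hypothesis in Section 4.2 is causal: that inappropriate antibiotic management is why these babies die.

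**The concern.** The fatality rates differ by organism: 18%, 8% and 5%, and by implication close to zero for CoNS. Deaths and survivors will therefore carry different organisms. If organisms also differ in susceptibility to the empiric regimen, cases and controls will differ in susceptibility even when mismatched therapy has no effect on any baby. The comparison would then partly measure which organisms kill, and Section 4.2 asks a different question.

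Organism group is present before empiric treatment begins and is not a consequence of mismatch, so it is a proper factor to control for. A selection rule that ignores it also spends many of the 100 control forms on infections that contribute few deaths, while Gram-negative survivors who could serve as controls go unused.

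**Working it through.** **1. The protocol's power figure.** Inputs (Section 7.2.1): 50 cases at 0.80, 100 controls at 0.95, 5% level (two-sided assumed).
- Pooled proportion: (40 + 95)/150 = 0.90.
- Standard error under the null: √[0.90 × 0.10 × (1/50 + 1/100)] = 0.0520.
- Standard error under the alternative: √[0.80 × 0.20/50 + 0.95 × 0.05/100] = 0.0606.
- z = (0.15 - 1.96 × 0.0520)/0.0606 = 0.79, so power is 78.7%. The stated 80% reproduces.

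**2. The protocol's number of deaths.**
- Gram-negative: 0.18 × 200 = 36.
- Other non-CoNS: 800 - 400 - 200 = 200 babies. Assuming the 5% to 8% rates apply to all of them, 10 to 16 deaths.
- Total 46 to 52. The stated figure of around 50 is reached with CoNS deaths near zero.

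**3. Organism mix.** With 50 deaths there are 750 survivors.
- Cases: 36/50 = 72% Gram-negative.
- Survivors: (200 - 36)/750 = 164/750 = 22% Gram-negative; 400/750 = 53% CoNS.
- An unmatched draw of 100 controls would hold about 22 Gram-negative and 53 CoNS.

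Sensitivity, with CoNS fatality assumed 0% to 5% and other non-CoNS 5% to 8%: the Gram-negative share of deaths runs from 36/(36 + 16 + 20) = 50% to 36/(36 + 10) = 78%. The 50% end implies 72 deaths, well above the stated 50. CoNS stay at 52% to 54% of survivors.

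**4. Possible confounding.** The documents give no susceptibility by organism, so the values below are assumed. Within each organism group susceptibility is the same in cases and controls, so there is no true effect. Assumed split (Gram-negative / other / CoNS): deaths 36/12/2, survivors 164/188/398. A positive difference is in the hypothesised direction (cases less susceptible).

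| Assumed susceptibility (Gram-negative / other / CoNS) | Cohort mismatch | Cases | Controls | Control minus case |
|---|---|---|---|---|
| 90% / 95% / 67.5% | (20 + 10 + 130)/800 = 20% | (32.4 + 11.4 + 1.35)/50 = 90.3% | (147.6 + 178.6 + 268.65)/750 = 79.3% | -11.0 points |
| 75% / 100% / 100% | 50/800 = 6.25% | (27 + 12 + 2)/50 = 82.0% | (123 + 188 + 398)/750 = 94.5% | +12.5 points |
| equal in all groups | any | equal | equal | 0 |

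With no CoNS deaths (36/14/0) the first row becomes 91.4% v 79.2%, or -12.2 points; the second is unchanged. Both mismatch rates lie within the 5-16% of Section 1 and the 10-20% of Section 2 taken together. The second row comes close to the protocol's 80% v 95% with no true effect, and a crude test would reject in about 66% of such studies. These are worked examples, not bounds.

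**5. Efficiency within Gram-negative infection**, by the formula of step 1 at 80% v 95%:
- 36 cases v 22 controls: pooled proportion 49.7/58 = 0.857; standard errors 0.0948 and 0.0813; z = (0.15 - 0.1857)/0.0813 = -0.44; power 33%.
- 36 cases v 72 controls: pooled proportion 0.90; standard errors 0.0612 and 0.0714; z = (0.15 - 0.1200)/0.0714 = 0.42; power 66%.

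The 72 controls would come from about 164 Gram-negative survivors.

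**The case against.** The 80% v 95% contrast is offered as an example of power and is not declared the primary analysis. Multivariable regression is planned, and Section 8.6 shows that pathogens and antibiograms are recorded. A covariate list is commonly left to the analysis plan, which is not at hand. All of this stands. A reader might infer that the study will rest on a crude comparison and so reach a wrong answer; the protocol does not say so. But the selection rule is fixed in the protocol, and a later covariate cannot supply Gram-negative controls that were never drawn.

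A reader might also infer that half the controls will certainly be CoNS. The 53% and 22% describe all survivors. Matching on birthweight category and hospital will move them by an amount that cannot be computed from the documents.

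The count of 36 in 50 is softer than it looks. Section 1 reports 18% Gram-negative mortality as attributable at 10 days, whereas cases are all deaths within 28 days. Deaths in CoNS babies may therefore be understated, which is why the 50% to 78% range is shown.

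Larger biases can be produced by assumption, but they need checking against the stated mismatch. CoNS at 50%, with 90% and 95% in the other groups, implies (20 + 10 + 200)/800 = 29% mismatch, above anything the protocol reports. Section 1 does not say whether its mismatch figure includes CoNS, so this check is itself approximate.

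Finally, matching on organism prevents the matched set from estimating organism as a risk factor. That is true, but pathogen and 28-day outcome are collected for the whole cohort, where it can still be estimated.

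**Conclusion.** The point holds as a fault in the control-selection rule. On the protocol's figures organism group is strongly tied to death: about 72% of cases Gram-negative (50% to 78% under varied rates) against about 22% of survivors, with about 53% of survivors CoNS. It confounds the susceptibility comparison wherever susceptibility differs by organism.

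The documents settle neither size nor direction. The -11 and +12.5 points rest on assumed susceptibilities, and the bias is zero if these are equal. It would therefore be too strong to say that the design creates, hides or reverses the association; it leaves each of these possible. The efficiency loss (33% against 66% power within Gram-negatives) does not depend on those assumptions, but it does rest on the unmatched survivor mix. The protocol's power arithmetic is sound. The rule should be changed.

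**What to change.** In Section 7.2.1:
- Add organism group (Gram-negative, CoNS, other) to the central selection of controls, frequency-matched two to one where survivors are available. With deaths split 36/12/2 this asks for 72, 24 and 4 controls, still 100 in total.
- Allow the hospital match to be relaxed where needed. If about 30 units take part there are roughly 164/30 = 5.5 Gram-negative survivors per unit against 72/30 = 2.4 needed, before birthweight is considered.
- Make organism group a required term in the multivariable (or conditional) logistic model for antibiotic appropriateness. Matching alone is not enough, especially where matches are incomplete.
- Report a non-CoNS comparison as a sensitivity analysis. It should not replace the main one, because Section 4.2 asks about bacterial infections generally.
- State the power within Gram-negatives (about 66% at two to one for 80% v 95%) beside the overall figure.

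The cost is small: pathogen is already recorded, selection is already central, and the number of control forms is unchanged. Some matches on all three factors will not exist and will rely on adjustment, and organism as a risk factor must be estimated from the full cohort.
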